## 7.4 Future Use of Stored Samples

Participants will be informed about and asked whether they agree to the long-term storage of their biological (stool and serum) specimens for use in future research as part of the informed consent process. Participants need not agree to this long-term storage component of the study to otherwise be consented to take part in the study. Participants who do agree to this will be consenting to the indefinite long-term storage of their remaining biological samples and data for use in future research, which unless further consent and IRB/IEC approvals are obtained, will be restricted to further knowledge about polio, the study vaccines, immune responses to the study vaccines, and the development of assays to measure these immune responses. No tests will be performed on the participant's genome. At study closure, these additional remaining samples will continue to be stored at the Polio and Picornavirus Laboratory Branch at the CDC, and/or if required, another PATH-designated biorepository that meets all current poliovirus containment requirements.

## 7.5 Biohazard Containment

As transmission of blood-borne pathogens can occur through contact with contaminated needles, blood, and blood products, appropriate blood and secretion precautions will be employed by all personnel in the drawing of blood and shipping and handling of all specimens for this study as recommended by the CDC. Risk mitigation procedures for the prevention of transmission of shed vaccine poliovirus during the collection, processing, storage, and transport of stool specimens will also follow CDC guidelines as stated in this protocol and detailed in the study-specific Laboratory Manual. All biological specimens will be transported using packaging mandated by United States Code of Federal Regulations (CFR) 42 Part 72. All dangerous goods materials, including diagnostic specimens and infectious substances, must be transported according to instructions detailed in the International Air Transport Association (IATA) Dangerous Goods Regulations. Biohazardous waste will be contained according to institutional, transportation/carrier, and all other applicable regulations.

All protocol specimens will be shipped using packing that meets requirements specified by the International Air Transport Association Dangerous Goods Regulations for UN 3373, Biological Substance, Category B, and Packing Instruction 650. Culture isolates, if obtained in this study, are to be shipped as specified for UN 2814 Category A Infectious Substances.

# 8 SAFETY ASSESSMENT AND REPORTING

## 8.1 Definitions

### 8.1.1 Adverse Event (AE)

An adverse event (AE) is any untoward medical occurrence in a participant after administration of the study vaccine and that does not necessarily have a causal relationship with the study vaccine. An AE can therefore be any unfavorable and unintended sign (including clinically significant abnormal laboratory finding), symptom, physical examination, or disease temporally associated with the use of the study vaccine, whether or not related to the study vaccine. This definition includes exacerbations of pre-existing conditions. Stable pre-existing conditions that do not change in nature or severity during the study are not considered AEs; however, these should be reported as part of the medical history.

**Solicited AEs** are pre-specific AEs that are common or known to be associated with vaccination that are actively monitored as potential indicators of vaccine reactogenicity. Investigators will not be required to

assess causality of solicited AEs if the onset is during the solicitation periods. Solicited AEs with onset after the solicitation period will be captured as unsolicited AEs.

For this trial, solicited AEs will be assessed on the day of study vaccination and for the 6 following days after each dose of study vaccine. Participants will be provided a memory aid to record the presence and severity or absence of solicited AEs. The memory aid may be accessed by smartphone or any device that connects to the internet. Solicited AEs with onset during the solicitation period that persist beyond the solicitation period will continue to be captured as solicited AEs.

The following specific solicited AEs will be monitored for this trial (Cohort 1):

- Fever (oral temperature  $\geq 38.0^{\circ}\text{C}$  or  $100.4^{\circ}\text{F}$ ). (The temperature comparison table with the different methods used can be found in the study MOP.)
- Chills
- Fatigue
- Headache
- Muscle aches/Myalgias
- Joint aches/Arthralgias
- Nausea
- Vomiting
- Abdominal pain
- Diarrhea

The following specific solicited AEs will be monitored for this trial (F Cohorts 2 and 3):

- Fever (axillary temperature  $\geq 37.5^{\circ}\text{C}$ )
- Vomiting
- Diarrhea
- Irritability
- Decreased feeding
- Decreased activity

**Unsolicited AEs** are any AEs reported spontaneously by the participant, observed by the study personnel during study visits or those identified during review of medical records or source documents.

In the absence of a diagnosis, abnormal physical examination findings or abnormal clinical safety laboratory test results that are assessed by the investigator to be clinically significant will be reported as an AE.

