## 2.3 Study Endpoints

### 2.3.1 Primary Endpoints:

#### Safety

- Frequency of serious adverse events (SAEs) from Day 1 study vaccination through the end of the study

- Frequency of solicited adverse events (AEs) for 7 days (day of study vaccination and 6 following days) after each dose of study vaccine
- Frequency of unsolicited AEs for 28 days (day of study vaccination and 27 following days) after each dose of study vaccine [including clinically significant aberrant safety monitoring laboratory values on Day 8 reported as AEs]

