## 4 STUDY POPULATION

### 4.1 Description of Study Population

The study population will include a total of 150 to 230 healthy adults, between the ages of 18 and 45 years, inclusive. Following informed consent, potentially eligible participants will continue to be screened until 150 to 230 adults have been found to be eligible, randomized and vaccinated. Participants withdrawn for any reason before vaccination will be replaced, participants withdrawn for any reason after vaccination will not be replaced. Enrollment into the study will be competitive in that clinical sites will enroll as many subjects as they can, until the overall study enrollment goal is achieved; the total number of trial participants enrolled study-wide does not change.

To be eligible for randomization and vaccination, participants must meet all the inclusion criteria and none of the exclusion criteria for the study. The investigator should always use good clinical judgement in considering a participant's overall eligibility based on the inclusion and exclusion criteria.

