**Table 4: Grading scale to grade the severity of solicited AEs**

Solicited AE	Grade	Definition
Fever (oral body temperature)	0	< 100.4°F (none)
	1	≥ 100.4°F to < 101.5°F
	2	≥ 101.5°F to < 102.7°F
	3	≥ 102.7°F

Diarrhea	0	None
	1	2 to 3 loose stools per 24 hours
	2	4 to 5 stools per 24 hours
	3	6 or more watery stools per 24 hours
Chills or fatigue or headache or myalgias or arthralgias or nausea or vomiting or abdominal pain	0	None
	1	Causes no or minimal interference with usual social & functional activities
	2	Causes greater than minimal interference with but does not prevent usual social & functional activities
	3	Causes inability to perform usual social & functional activities

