### **13.6 Risk and Benefits**

Participants will not derive any direct benefits from their participation in this research study. Participants may indirectly benefit from the clinical assessments (medical history, physical examination, and routine clinical safety laboratory tests) conducted at screening and during the study. If the participant is found to have any newly diagnosed medical condition or infection, the investigator will ensure that the participant is provided with appropriate and adequate referrals within the health care system. Participation in this study will hopefully contribute to development and eventual deployment of a vaccine to address a global public health concern.

Preclinical testing of the two nOPVs (nOPV1 and nOPV3) to be assessed in this study have not identified specific, inherent risks of these products. There are currently no clinical safety data for nOPV1 or nOPV3 as they have not yet been tested in humans; however, a similar nOPV, against type 2 poliovirus (nOPV2), has been assessed in phase 1 and 2 trials in adults in Belgium and in a phase 2 trial in young children and infants in Panama, and the vaccine has been well-tolerated and no specific safety concerns have been identified.

As the nOPVs are derived from Sabin OPV, the risks associated with Sabin OPV must be considered possible for these products. There are certain symptoms that have commonly been associated with immunizations in general, and if they do occur, are usually not severe in intensity and transient in nature. Consequently, in early clinical trials of investigational vaccines, these symptoms are typically considered as risks and are solicited as potential AEs in the first week following immunization. As with other similar vaccines, these events have also been observed following immunization with Sabin OPV; therefore, in this study, the AEs that will be actively solicited in the one week following administration of the study vaccines include such events, specifically, fever, chills, fatigue, headache, myalgias (muscle aches), arthralgias (joint aches), nausea, vomiting, abdominal pain, and diarrhea.

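### Section 8.1.1 contradicts the rest of the protocol on which events are solicited: the adult list goes to Cohort 1 only, an ill-fitting list to Cohorts 2 and 3, and none to Cohort 4

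*Protocol*

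**What the plan says.** Section 2.3.1 makes this a primary endpoint: "Frequency of solicited adverse events (AEs) for 7 days (day of study vaccination and 6 following days) after each dose of study vaccine". It names no symptoms and no cohorts, so the content comes from section 8.1.1.

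Section 8.1.1 gives two separately headed lists.

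- The first opens "The following specific solicited AEs will be monitored for this trial (Cohort 1" and holds ten events: fever (oral, 38.0 °C / 100.4 °F or above), chills, fatigue, headache, myalgia, arthralgia, nausea, vomiting, abdominal pain and diarrhea.
- The second opens "The following specific solicited AEs will be monitored for this trial (F Cohorts 2 and 3" and holds six: fever, vomiting, diarrhea, irritability, decreased activity and "Decreased feeding". Its fever item begins "Fever (axillary temperature" and starts at 37.5 °C.

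Cohort 4 appears in neither heading.

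Elsewhere the protocol describes one adult set. Section 13.6 says what will be solicited after the study vaccines: "specifically, fever, chills, fatigue, headache, myalgias (muscle aches), arthralgias (joint aches), nausea, vomiting, abdominal pain, and diarrhea". Section 8.3 sends every solicited event to Table 4, which has rows for those ten only and whose first row is "Fever (oral body temperature"), graded from 100.4 °F. Section 6.9 has participants take their temperature orally for reactogenicity. On the population, section 4.1 states: "The study population will include a total of 150 to 230 healthy adults, between the ages of 18 and 45 years, inclusive".

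**The concern.** The four cohorts differ by prior vaccination (IPV only or OPV-containing) and by vaccine type. They do not differ by age, so nothing in the design calls for a separate symptom list in Cohorts 2 and 3. Irritability and decreased feeding are not natural diary items for healthy adults.

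A site cannot follow every section at once. If it follows 8.1.1, it collects events that Table 4 cannot grade and uses a temperature route that section 6.9 does not prescribe. If it follows 6.9, 8.3 and 13.6, it departs from 8.1.1. What is at stake is whether one primary safety endpoint of a first-in-human trial is measured with the same instrument in all cohorts, and whether the pooled summaries by vaccine type can be interpreted.

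**Working it through.** **Who is affected.** Cohort sizes come from the Study Schema in section 3: Cohort 1, 30 to 40; Cohort 2, 45 to 75; Cohort 3, 30 to 40; Cohort 4, 45 to 75.

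- Plan's own total: 30 + 45 + 30 + 45 = 150 and 40 + 75 + 40 + 75 = 230. Both are reproduced.
- Conflicting list (Cohorts 2 and 3): (45 + 30)/150 = 50.0%; (75 + 40)/230 = 50.0%.
- No list in 8.1.1 (Cohort 4): 45/150 = 30.0%; 75/230 = 32.6%.
- Adult list assigned (Cohort 1): 30/150 = 20.0%; 40/230 = 17.4%.
- By vaccine, 8.1.1 assigns the adult list to 15 of 45 (33%) to 20 of 70 (29%) nOPV1 recipients and to no nOPV3 recipient.

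**What differs between the lists.**

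- In both: vomiting and diarrhea. Fever is also in both, with a different route and threshold.
- Only in the Cohort 1 list: chills, fatigue, headache, myalgia, arthralgia, nausea and abdominal pain (seven of ten).
- Only in the Cohort 2 and 3 list: irritability, decreased feeding and decreased activity (three of six).

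**Grading.** Table 4 has no row for those last three events. The DAIDS scale named in section 8.3 is reserved for events other than solicited and laboratory ones, so it does not fill the gap. Without a grade they cannot count toward the grade 3 solicited pause rule in section 9.3. For fever, 37.5 °C is 37.5 × 1.8 + 32 = 99.5 °F, which Table 4 would class as grade 0 if the reading were taken at face value. Section 8.1.1 mentions a temperature comparison table in the MOP, which may convert routes but is not shown.

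**Pooled comparison.** Section 11.5.5 sets Groups 1 + 3 against Groups 2 + 4. Cohort 1 is randomized 1:1 and Cohort 2 is randomized 2:1, so the two pools contain different shares of Cohort 1.

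- nOPV1 pool: 15/(15 + 30) = 33.3%; at maximum, 20/(20 + 50) = 28.6%.
- mOPV1 pool: 15/(15 + 15) = 50.0%; at maximum, 20/(20 + 25) = 44.4%.

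Suppose the two vaccines are equally reactogenic, and the adult list finds any event in a proportion *a* while the short list finds one in *s*. The spurious pooled difference (mOPV1 minus nOPV1) is then (difference in Cohort 1 share) × (*a* − *s*). The share difference is 50.0% − 33.3% = 16.7 points at minimum size and 44.4% − 28.6% = 15.9 points (unrounded) at maximum. The protocol gives no value for *a* − *s*, so these are assumptions:

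- *a* − *s* = 10 points: 1.7 (minimum size) or 1.6 (maximum size) points.
- *a* − *s* = 30 points, for example 50% and 20%: 30.0% against 35.0%, or 28.6% against 33.3%; about 5 points.
- *a* − *s* = 50 points: 8.3 or 7.9 points.

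The sign favors nOPV1 whenever the longer list finds more. For type 3, Cohort 3 with the short list would be pooled with Cohort 4, which has none.

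**The case against.** The strongest reply is that the rest of the protocol agrees with itself. Section 13.6, Table 4 and section 6.9 all point to one adult set with oral temperature, so a careful site might apply it throughout. The second list looks like text carried over from a study with other cohorts, though that is an inference. The memory aid and eCRF are not shown and may be right. This stands as a limit on what can be said about data actually collected. It does not resolve the contradiction, because 8.1.1 is where the solicited events are defined.

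Three further points stand and narrow the consequences.

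- Fisher tests for solicited events are run within cohorts (section 11.5.5.1). In Cohorts 1, 2 and 3 both arms share one list, so those randomized comparisons stay like-for-like.
- The seven missing events could still be reported in Cohorts 2 and 3 as unsolicited events for 28 days, graded on the DAIDS scale, and counted under the pause rule for grade 3 unsolicited events. Spontaneous report is less sensitive than a diary, but the events are not lost to safety oversight.
- In Cohort 4, the unrestricted set in 13.6 and Table 4 meets no competing list.

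A reader might infer that the primary endpoint is wrong for about 80% of participants (120/150 = 80.0% to 190/230 = 82.6%). The documents do not support that. The endpoint text names no symptoms, and the figure adds together two different problems: a conflicting list in half the participants and a missing assignment in about a third. Nor does section 13.6 settle the fever definition, since it gives neither route nor threshold; those come from Table 4 and from the Cohort 1 list itself.

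**Conclusion.** The point holds as an internal contradiction that must be resolved. Section 8.1.1 conflicts with sections 6.9, 8.3 (Table 4) and 13.6 on which events are solicited and how fever is measured. The conflict covers 50% of participants through an ill-fitting list and a further 30% to 33% through the absence of one; these shares assume all cohorts fill to the minimum or all to the maximum.

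Read literally, the text would leave seven adult events unsolicited in Cohorts 2 and 3, leave three listed events ungradable and outside the solicited pause rule, and mix instruments in the pooled summaries. The bias of about 5 points in the type 1 pool is an illustration under an assumed 30-point gap in detection, not an estimate. Whether any data are affected depends on the memory aid and eCRF. Nothing shows that different lists were intended.

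**What to change.** In section 8.1.1, remove the second list and the Cohort 1 qualifier on the first. State that the ten events that Table 4 can grade, with oral temperature, are solicited in all four cohorts after each dose. Sections 6.9, 8.3 and 13.6 then agree with it unchanged.

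Check the memory aid and eCRF against the corrected list. If they already carry the ten events everywhere, the cost is a protocol amendment or clarification memo. If they were built from 8.1.1 as written, they must be rebuilt and the memory aid becomes somewhat longer for Cohorts 2 to 4. Any data already collected on the shorter list should then be identified and kept apart in the pooled summaries.

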### **8.1.2 Adverse reaction / Suspected Adverse Reaction (21CFR Part 312.32)**

**Suspected adverse reaction** is any adverse event for which there is a reasonable possibility that the vaccine caused the adverse event. For the purposes of IND safety reporting, "reasonable possibility" means there is evidence to suggest a causal relationship between the vaccine and the adverse event. Suspected adverse reaction implies less certainty about causality than adverse reaction, which means any adverse event caused by a vaccine.

**Adverse reaction** is any adverse event caused by the vaccine. Adverse reactions are a subset of suspected adverse reactions for which there is reason to conclude that the vaccine caused the event.

**Unexpected adverse event or unexpected suspected adverse reaction** refers to an event or reaction that is not listed in the IB or is not listed at the specificity or severity that has been observed.

### 8.1.3 Serious Adverse Event (SAE)

Serious adverse event is any adverse event that results in any of the following outcomes:

- Death
- Is life-threatening (life-threatening means that the study participant was, in the opinion of the investigator or PATH, at risk of death at the time of the event; it does not refer to an event which hypothetically might have caused death if it were more severe)
- Requires inpatient hospitalization or prolongation of existing hospitalization
- Results in persistent or significant incapacity or substantial disruption of the ability to conduct normal life functions
- Congenital anomaly or birth defect
- Important medical event that may not result in one of the above outcomes, but based upon appropriate medical judgment, may jeopardize the health of the study participant, and require medical or surgical intervention to prevent one of the outcomes listed above

**Suspected unexpected serious adverse reaction (SUSAR)** is any suspected adverse reaction that is both unexpected and serious.

## 8.2 Reporting Period and Parameter

Safety events are reported from the time of signing the ICF through each participant's completion of the study 168 days after their Day 1 study vaccination. Specifically, solicited AEs will be collected for 7 days (day of study vaccination and 6 following days) after each dose of study vaccine. If a solicited AE started during the 7 days post-vaccination and continues beyond the 7 days, it will continue to be reported as a solicited AE. Unsolicited AEs will be collected for 28 days (day of study vaccination and 27 following days) after each dose of study vaccine. SAEs will be collected from Day 1 study vaccination through the end of the study (Day 169 Telephone visit).

Any untoward medical occurrence after signing the ICF but before receipt of study vaccine, although not to be reported as an AE, if it is assessed as related to participation in the study, must still be reported by email to PATH within 3 days of awareness.

Due to uncertainties around the COVID-19 pandemic and the potential for stay-at-home orders, if a subject is unable to come to the clinic for a visit, the scheduled and applicable safety assessments may be conducted by telephone.

## 8.3 Severity of Adverse Events

### Solicited AEs:

The severity of all solicited AEs will be graded based on the grading scale in [Table 4](#) below.

**Table 4: Grading scale to grade the severity of solicited AEs**

Solicited AE	Grade	Definition
Fever (oral body temperature)	0	< 100.4°F (none)
	1	≥ 100.4°F to < 101.5°F
	2	≥ 101.5°F to < 102.7°F
	3	≥ 102.7°F

Diarrhea	0	None
	1	2 to 3 loose stools per 24 hours
	2	4 to 5 stools per 24 hours
	3	6 or more watery stools per 24 hours
Chills or fatigue or headache or myalgias or arthralgias or nausea or vomiting or abdominal pain	0	None
	1	Causes no or minimal interference with usual social & functional activities
	2	Causes greater than minimal interference with but does not prevent usual social & functional activities
	3	Causes inability to perform usual social & functional activities

**Abnormal clinical safety laboratory test results reported as AEs:**

The severity of abnormal clinical safety laboratory test results reported as AEs will be graded based on the grading scale in [Table 5](#) below. The table is adapted from the FDA Guidance for Industry: Toxicity Grading Scale for Healthy Adult and Adolescent Volunteers Enrolled in Preventive Vaccine Clinical Trials (September 2007). In the absence of a diagnosis, any clinical safety laboratory test result that meets the definition of an SAE as determined by the investigator (e.g., life-threatening) must be reported as an SAE.

**Table 5: Grading scale to grade the severity of abnormal clinical safety laboratory test results reported as AEs**

Parameter	Grade 1 (Mild)	Grade 2 (Moderate)	Grade 3 (Severe)
Hemoglobin [Female] (g/dL)	11.0 – 12.0	9.5 – 10.9	< 9.5
Hemoglobin [Female] change from baseline value (g/dL)	Any decrease – 1.5	1.6 – 2.0	> 2.0
Hemoglobin [Male] (g/dL)	12.5 – 13.5	10.5 – 12.4	< 10.5
Hemoglobin [Male] change from baseline value (g/dL)	Any decrease – 1.5	1.6 – 2.0	> 2.0
WBC Increase (cell/mm  )	10,800 – 15,000	15,001 – 20,000	> 20,000
WBC Decrease (cell/mm  )	2,500 – 3,500	1,500 – 2,499	< 1,500
Lymphocytes Decrease (cell/mm  )	750 – 1,000	500 – 749	< 500
Neutrophils Decrease (cell/mm  )	1,500 – 2,000	1,000 – 1,499	< 1,000
Eosinophils (cell/mm  )	650 – 1,500	1,501 – 5,000	> 5,000
Platelets Decreased (cell/mm  )	125,000 – 140,000	100,000 – 124,000	< 100,000
Creatinine (mg/dL)	1.5 – 1.7	1.8 – 2.0	> 2.0
ALT increase by factor	1.1 – 2.5 x ULN*	> 2.5 – 5.0 x ULN*	> 5.0 x ULN*
Total bilirubin increase by factor	1.1 – 1.5 x ULN*	> 1.5 – 2.0 x ULN*	> 2.0 x ULN*

\*ULN = upper limit of normal

